Mirthful laughter and muscle soreness/pain

NCT02896075

April 7, 2017

Study Protocol

Participants

Forty adults (15 men and 25 women) 20-40 years of age were recruited. Participants were included if they were apparently healthy, normotensive, and free of musculoskeletal disease. Participants were excluded if they had known cardiovascular or musculoskeletal disease or if their pain tolerance was not reachable in a blunt force test on the quadriceps (maximal pressing force allowed by the IRB was 245 N). Participants were instructed to keep their normal daily routine including caffeine consumption throughout the study period to prevent the effects of lifestyle factors on pain tolerance measurements. The Institutional Review Board approved the study, and a written informed consent was obtained from all participants. The study was registered at the National Institutes of Health (ClinicalTrials.gov).

Preliminary study to evaluate various pain tolerance tests

Hemodynamic factors are known to influence pain perceptions and pain responses (Bruehl & Chung, 2004) as the brain regions regulating the cardiovascular system are known to overlap substantially with those that contribute to anti-nociception (Randich & Maixner, 1984). In order to select the optimum pain tolerance protocol that would not evoke substantial hemodynamic responses, changes in blood pressure and heart rate in response to 3 commonly-used pain tolerance tests (blood pressure cuff occlusion, blunt force application on muscles, and cold pressor test) were compared. Participants were instructed to lie supine with a beat-by-beat blood pressure monitor (Portapres, Finapres Medical Systems, Enschede, Netherlands) that was placed on the middle phalanx of the middle finger on the left hand. The Portapres was connected to the WinDaq data acquisition software (DATAQ Instruments, Akron, OH) to record heart rate and blood pressure for later analysis.

A load cell (Transducer Techniques, Temecula, CA) attached to a pan head screw and metal handle was used to determine the load placed on the quadriceps of each participant. The force transducer applied blunt force and measured the force by running through an amplifier (TMO-2, Transducer Techniques, Temecula, CA) connected to our data acquisition software (WinDaq). Blunt force was steadily increased until the participant indicated that the pain was not tolerable, at which point the test was terminated. The blunt force was applied half way between the anterior superior iliac spine and the top of the patella. The specific spot was marked in order to avoid testing directly on the same exact spot that could inflict residual tenderness. The rate of increases in applied force was controlled through feedback on the WinDaq data acquisition system.

For the blood pressure cuff pain test, a standard blood pressure cuff was placed on the right upper arm. The cuff was gradually inflated at 15 mmHg per second until the participant indicated that they were at the limit of their pain tolerance. Per the IRB guideline, the maximum blood pressure was set at 300 mmHg. The cold pressor test was performed with the participants submerging their hand up to their wrist in ice water of about 4 °C. Participants were told to remove hand when they reached their pain tolerance.

Main experimental protocol

The main study was conducted using a randomized controlled cross-over approach. Participants reported to the laboratory a total of seven times. Participants underwent a preliminary testing session followed by three visits each for the two video watching interventions. The interventions were separated by a minimum of one week as a washout. Each intervention included one day of inducing muscle soreness in one leg through eccentric muscle contractions (see below), a second day of testing muscle soreness and pain tolerance and watching a 30-minute video (either a comedy or documentary), and a third day of testing muscle soreness and pain tolerance again to see if the effects of the video viewing persisted the next day (i.e., twenty-four hours after the video viewing).

The second intervention was identical to the first intervention except that muscle soreness was induced on the contralateral leg and the video was switched to either comedy or documentary. The orders of the videos and legs were randomized by a research assistant flipping a coin, and participants watched a randomly-assigned video. If the video was a comedy, the participants picked stand-up comedians of their choice in order to meet with their individual preference of comedy/humor. The video was watched for 30 minutes with two other people in

the room to make it a social setting to induce greater degree of laughter. When the video was a documentary, an uninteresting serious documentary was chosen by the investigators.

Eccentric exercise

Participants began with a five-minute warm-up at 50 W on a cycle ergometer (Monarch Exercise, Vansbro, Sweden). Participants were then secured to the isokinetic dynamometer chair in a seated position with chest and waist straps (Biodex System 2, Shirley, NY). The movement began at a speed of 45 degrees/second at a knee angle of 90 degrees. The participants were instructed to resist maximally until full flexion was reached and completed 12 sets of 10 repetitions of eccentric maximal voluntary actions. Participants aimed for 70% or better of the previously-tested one repetition maximum for the eccentric phase. Exercise sets were separated by one minute of rest. This protocol has been utilized successfully in previous studies to elicit delayed onset muscle soreness (Armstrong, Warren, & Warren, 1991; Prou, Guevel, Benezet, & Marini, 1999; Vassilis et al., 2008).

Body composition

The seven-site skinfold assessment was utilized to estimate body fat percentage using Lange skinfold calipers (Cambridge Scientific, Cambridge, MA). Body fat level was collected primarily as a descriptive variable but could potentially contribute to pain tolerance due to the association between body fat and inflammatory mediators (Gustafson, 2010) that could sensitize nociceptors to pain (Marchand, 2008).

Muscle strength

A reduction in muscle strength is an objective indication of muscle soreness (Byrnes & Clarkson, 1986). Knee extensors of both legs were tested for maximum strength using the isokinetic dynamometer (Biodex System 2, Shirley, NY). Both the concentric and eccentric

phases of the strength test were set at a speed of 60 degrees/second. Subsequently, isometric (static) muscle strength tests were performed. The lever was locked at 60 degrees and then at 90 degrees, and the participant was instructed to try to extend the leg and hold it for 5 seconds.

Pain

The visual analog scale pain score (VAS) is an established instrument for the assessment of subjective pain (Jensen, Karoly, & Braver, 1986) that has been found to be reliable (Price, McGrath, Rafii, & Buckingham, 1983). It is a scale from 0 to 10 showing faces and descriptions of what participants may feel (Jensen et al., 1986). Participants picked the number (i.e., pain score) that corresponded best to how their sore leg felt. Participants also had their pain tolerance measured using the force test as an objective measure.

Mood and psychological state

The Coping Humor Scale (CHS) and the Situational Humor Response Questionnaire (SHRQ) were administered to all the subjects (Martin, 1996). The Positive and negative affect schedule (PANAS) was administered before and after watching the video to evaluate changes in mood state. High negative affect is characterized by subjective distress and unpleasurable engagement, and low negative affect by the absence of these feelings. Positive affect represents the extent to which an individual experiences pleasurable engagement with the environment (Watson, Clark, & Tellegen, 1988).

Laughter

In order to quantify the amount of laughter, a Pneumotrace II respiration transducer (UFI, Morro Bay, CA) was worn above the umbilical region while watching the videos. The respiration transducer was attached to the WinDaq data acquisition system (DATAQ Instruments, Akron,

OH) to record the data. The irregular respiratory pattern was taken as indications of laughter as previously described (Bloch, Lemeignan, & Aguilera-T, 1991; Svebak, 1975).

Statistical analyses

Descriptive characteristics were expressed as means \pm SEM. Paired t-tests were conducted between the various outcomes of the comedy and documentary treatments with the probability level set at $p<0.05$. To compare physiological changes caused by each pain tolerance test, linear mixed models were used. A random intercept was included for each participant since the experiment was repeated measures. ANOVA tables for each fitted model were constructed. In the case of significance, multiple comparisons were performed using the Bonferroni method. To control for important covariates and to investigate significant predictors of pain tolerance, linear mixed model analyses that include fixed and random effects were used. The linear mixed model included fixed and random effects, to predict the pain tolerance. The fixed component described the sample's relationship between the covariates, predictors, and pain tolerance while the random component described the variation within each participant. The inclusion of a random intercept for each participant in the mixed model was justified because of the large variance in pain tolerance. Predictor variables included leg, time, and treatment, while covariates included sex, SHRQ, CHS, PANAS scores, and body fat percentage. A simple ordinary least squares regression was used to investigate if a relationship exists between the time spent laughing and the change in pain tolerance. To determine the total variability in pain tolerance, the intraclass correlation coefficient (ICC) was calculated.

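### The comedy-versus-documentary analysis of this two-period crossover names no period effect: any first-to-second shift costs precision and, if the video orders are uneven, biases the estimate

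*Combined protocol and SAP*

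**What the plan says.** Under Main experimental protocol: "The main study was conducted using a randomized controlled cross-over approach". The two interventions follow the same sequence of visits: "The second intervention was identical to the first intervention except that muscle soreness was induced on the contralateral leg", and the video is switched. On spacing, "The interventions were separated by a minimum of one week as a washout". On allocation, "The orders of the videos and legs were randomized by a research assistant flipping a coin"; no blocking or other balancing is described, and the number in each order is not given.

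Under Statistical analyses, the treatment comparison is: "Paired t-tests were conducted between the various outcomes of the comedy and documentary treatments". A linear mixed model with a participant random intercept is also planned for pain tolerance. Its terms are given as "Predictor variables included leg, time, and treatment", plus sex, the humour and affect scales and body fat as covariates. *Time* is not defined. Period, order and sequence are not named in any analysis.

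**The concern.** Each participant goes through the maximal eccentric exercise and the tolerance tests twice. If responses differ between the first and second intervention for reasons unrelated to the video, such as familiarisation, each comedy-minus-documentary difference carries that shift. The sign is positive for people who saw comedy second and negative for those who saw it first. A plain paired t-test cannot separate the shift from the treatment effect or from error.

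Other features of the plan do not remove it:

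- Leg does not identify period, because leg order is itself randomised.
- The random intercept removes differences between people, not a shift within a person.
- The washout is aimed at carryover, not at familiarisation.

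Two consequences follow. With an even split, the shift inflates the error term and the test is conservative and loses power. With an uneven split, part of the shift enters the estimate, and a reader who does not know the split cannot tell how much.

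**Working it through.** The documents contain no sample size calculation, SD, effect size or order split, so there is no stated figure to reproduce.

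**Inputs from the documents.** Number recruited: "Forty adults (15 men and 25 women) 20-40 years of age were recruited" (Participants). Significance level 0.05 (Statistical analyses). Order by coin flip (Main experimental protocol).

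**Assumptions.** All 40 complete both interventions; two-sided testing; 80% power when there is no shift; shifts of 0.25 to 1 SD. The unit is the SD of the comedy-minus-documentary difference within a video order.

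**Model.** Let τ be the treatment effect and π the second-minus-first shift. The difference d has mean τ + π for comedy second (n2 people) and τ − π for comedy first (n1 people), with error SD 1 and N = n1 + n2.

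- Unadjusted mean: τ + π(n2 − n1)/N, so the bias given the split is π(n2 − n1)/N.
- Its estimated SE: √{[1 + π²(1 − ((n2 − n1)/N)²)]/N}.
- Averaged over coin flips, d has SD √(1 + π²) and mean τ.

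**Step 1: power averaged over coin flips.** With 40 people, 80% power at π = 0 needs τ = 0.454 SD. Noncentral t with SD √(1 + π²) gives:

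| Shift (SD) | 0 | 0.25 | 0.5 | 0.75 | 1 |
|---|---|---|---|---|---|
| Paired t-test power | 80.0% | 77.6% | 70.7% | 61.1% | 50.9% |

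Simulating the coin flips agrees to within half a point, with type I error of 5.0% to 5.1% and no average bias. With 30 to 40 completers and the baseline held at 80%, the figures are the same.

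**Step 2: how uneven the split may be.** From Binomial(40, 0.5): exactly 20:20, 12.5%; 24:16 or worse, 26.8%; 25:15 or worse, 15.4%.

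**Step 3: bias given the split.** At 24:16, (n2 − n1)/N = 8/40 = 0.20. At 25:15 it is 10/40 = 0.25.

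- Shift 0.5 SD: bias 0.5 × 0.20 = 0.10 SD and 0.5 × 0.25 = 0.125 SD. The SE at 24:16 is √{[1 + 0.25 × 0.96]/40} = √(1.24/40) = 0.176 SD, and it is also 0.176 SD at 25:15.
- Shift 0.25 SD: bias 0.05 and 0.0625 SD; SE √(1.06/40) = 0.163 SD at 24:16 and also 0.163 SD at 25:15.

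**Step 4: type I error of the paired t-test given the split** (simulation, 400,000 runs per cell).

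| Shift (SD) | 20:20 | 24:16 | 25:15 |
|---|---|---|---|
| 0.25 | 4.3% | 5.4% | 6.0% |
| 0.5 | 2.9% | 6.2% | 8.1% |

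Repeat runs agree to about 0.2 points. At 25:15 with a 0.5 SD shift, power is 92% or 44% depending only on the direction of the shift.

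**Step 5: does leg rescue it?** Regressing d on the leg contrast without period, with leg order assumed independent of video order, gives at a 0.5 SD shift a bias of 0.10 SD and type I error of 6.1% at 24:16, and 0.125 SD and 8.1% at 25:15. That is essentially unchanged.

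**Step 6: with a period term.** The estimate is the unweighted mean of the two order-specific mean differences, with variance (1/n1 + 1/n2)/4 and 38 degrees of freedom. At 25:15 the SE is √[(0.0400 + 0.0667)/4] = 0.163 SD. Bias is 0 and type I error 5.0% at all three splits. Power is 79.9% (20:20), 78.3% (24:16) and 77.4% (25:15), whatever the shift.

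**The case against.** The strongest reply is that the harm is unproven and may be small. Shifts of 0.5 SD and above exceed the 0.454 SD treatment effect used as the baseline, and nothing in the documents supports a shift that large. At 0.25 SD the averaged power is 77.6% unadjusted against 78.9% adjusted, a gain of about 1.3 points, while adjusting costs 1.1 points if there is no shift. The break-even is at about 0.17 SD. For every split up to 23:17, which covers 73% of coin-flip outcomes, type I error stays below 5% at both 0.25 and 0.5 SD. Over the randomisation as a whole there is no bias.

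The design may also shrink the shift. There is a preliminary session, the second intervention uses the other leg, and the washout lasts at least a week. Some outcomes look like within-intervention changes, in which a level shift cancels: the regression concerns "the time spent laughing and the change in pain tolerance", and the affect scale is given before and after the video. Finally, *time* might be coded by visit or intervention and so absorb the shift.

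All of this stands as a limit on weight, and none of it removes the point. The section does not say which of the outcomes put to the t-test are levels and which are changes. Pain tolerance and soreness are measured on the video day and again the next day, so comparisons of levels are plausible. Even if *time* covers period, the mixed model is for pain tolerance only; for other outcomes, such as the pain score, the t-test is the only stated treatment comparison.

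**Conclusion.** The concern holds. The paired t-tests have no period term. For the mixed model, what can be said is that none is named and *time* is undefined.

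The main consequence is lost precision: from about 2 points of power at a 0.25 SD shift to about 29 points at 1 SD, averaged over the coin flips. The second is bias given an uneven split, 0.10 to 0.125 SD at 24:16 to 25:15 with a 0.5 SD shift, where type I error is about 6% to 8%. These sizes rest on the assumed shifts, 40 completers and an 80% power baseline. If the shift is near zero, or an outcome is analysed as a within-intervention change and the shift is a pure level shift, the harm is nil. The change is worth making because it is cheap and protects against an unknown; the omission does not by itself invalidate the trial.

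**What to change.** - Add period (first or second intervention) as a fixed effect in the mixed model.
- Replace the paired t-test with the period-adjusted two-sequence comparison: the unweighted mean of the comedy-minus-documentary differences in the two video orders, with its pooled SE.
- Define *time*, state which outcomes are levels and which are within-intervention changes, and report the number in each video order.

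The cost is one degree of freedom and some wording. If there is no shift, power falls from 80.0% to 78.9% averaged over the possible splits: by 0.1 point at 20:20, 1.7 at 24:16 and 2.6 at 25:15. No new data are needed, only the order that each participant was assigned, so it can be done as a re-analysis.

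### The comedy-versus-documentary paired t-tests do not define the compared quantity, and neither a post-video value nor a plain change score adjusts for the same-session pre-video reading

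*Combined protocol and SAP*

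**What the plan says.** Under Main experimental protocol, "The main study was conducted using a randomized controlled cross-over approach". Each intervention takes three days: eccentric exercise on one leg, then "a second day of testing muscle soreness and pain tolerance and watching a 30-minute video (either a comedy or documentary"), then "a third day of testing muscle soreness and pain tolerance again to see if the effects of the video viewing persisted the next day". The second intervention uses the other leg and the other video, after a washout of at least one week. A coin flip set the orders of videos and legs.

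The Statistical analyses section gives one direct test of the two videos: "Paired t-tests were conducted between the various outcomes of the comedy and documentary treatments". It names no time point, change score or baseline.

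The same section describes a linear mixed model for pain tolerance. Its predictors are leg, time and treatment; its covariates are sex, the two humor scales, PANAS and body fat; it has a random participant intercept. A separate regression looks for a relationship "between the time spent laughing and the change in pain tolerance".

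PANAS is the only measure that the plan explicitly places both before and after the video (Mood and psychological state). For pain tolerance, a before-and-after pair is implied by the time predictor and by that regression. For the VAS pain score, the day-2 timing relative to the video is not given.

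**The concern.** Pairing removes what is stable about a participant. It does not remove what differs between that participant's two sessions before the video starts: which leg is sore, how hard that exercise bout was, and how sore the leg became that week. A reading taken on day 2 before the video captures much of this.

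The plan does not say that the t-tests use this reading, and the two natural readings of the sentence handle it differently. A post-video comparison leaves the session differences in the error. A change score subtracts them in full, which over-corrects when the pre-video reading predicts the post-video reading only weakly. The two can give different answers from the same data, and the plan does not fix which one is reported. The plan contains no sample-size or power calculation, so there is no stated margin to absorb lost precision.

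**Working it through.** The plan states no effect size, SD or power, so there is no figure to reproduce. What follows is an illustration under stated assumptions.

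**Inputs**
- Pairs: 40, from "Forty adults (15 men and 25 women) 20-40 years of age were recruited" (Participants), assuming that all complete; no dropout figure is given.
- Significance level: 0.05 (Statistical analyses). Sidedness is not stated; two-sided is assumed.
- Effect: 0.4 SD of the comedy-minus-documentary difference. Assumed.
- r: correlation between the paired pre-video difference and the paired post-video difference. Not in the documents; 0 to 0.7 is shown.
- Equal variance of the paired differences before and after the video. Assumed.

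**Step 1: variance of the estimated video effect, relative to a post-only paired test**
- Post-video only: 1
- Change score: 2(1 − r)
- Adjusted for the pre-video difference: 1 − r², before the cost of estimating extra terms

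At r = 0.3, the change score gives 2 × 0.7 = 1.40 and adjustment gives 1 − 0.09 = 0.91. The change score equals post-only at r = 0.5, where 2 × 0.5 = 1.00.

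**Step 2: power with 40 pairs**

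Post-only and change-score figures use the noncentral t with 39 degrees of freedom and noncentrality 0.4 × √40 / √(relative variance). For post-only this is 0.4 × 6.325 = 2.53, which gives 69.4%. The adjusted figures come from simulating the regression itself, with slope and terms estimated (20,000 trials per cell, no true period or leg effect).

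| r | Change: variance | Adjusted: variance | Post-only power | Change power | Adjusted: baseline + period | Adjusted: baseline + period + leg |
|---|---|---|---|---|---|---|
| 0 | 2.00 | 1.00 | 69% | 41% | 67% | 66% |
| 0.2 | 1.60 | 0.96 | 69% | 50% | 69% | 68% |
| 0.3 | 1.40 | 0.91 | 69% | 55% | 71% | 70% |
| 0.5 | 1.00 | 0.75 | 69% | 69% | 79% | 78% |
| 0.7 | 0.60 | 0.51 | 69% | 89% | 92% | 91% |

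Residual degrees of freedom fall from 39 to 37 with slope and period, and to 36 with leg as well.

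**Step 3: is the post-only test biased?** In simulation with no video effect (20,000 trials at each of r = 0.3, 0.5 and 0.8), its type I error was 0.048 to 0.051, which is nominal. Among trials whose mean pre-video difference happened to exceed 1.5 standard errors, false positives were about 7%, 13% and 25% at those three values of r. This is conditional chance imbalance, not systematic bias.

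**Step 4: does the mixed model resolve it?** Suppose one pre-video and one post-video reading per session both enter as rows with main effects only. The treatment coefficient is then the average of the two paired differences. With no expected difference before the video and 0.60 after it, that is (0 + 0.60)/2 = 0.30, and simulation returned 0.30. The leg term removes an average difference between legs, but not how sore a given leg was on a given day. The model is specified for pain tolerance only, so VAS is left with the t-test.

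**The case against.** The strongest reply is that an unadjusted paired test in a randomized crossover is valid, and that leaving out the baseline is a choice about efficiency. That stands: overall type I error is nominal.

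Four stronger readings are tempting, and the documents do not support them.

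- **A reader might infer that the plan ignores the pre-video reading.** The sentence leaves the outcome undefined, and a t-test on change scores fits it equally well. For PANAS, the plan's stated aim is to evaluate change in mood.
- **A reader might infer that the video effect is biased.** Video and leg orders were randomized, so a pre-video difference arises by chance.
- **A reader might infer that leg differences are left unhandled everywhere.** Leg is a predictor in the pain-tolerance mixed model. The gap there is narrower: no treatment-by-time term and no baseline covariate, and no such model for VAS.
- **A reader might infer that adjustment can only help.** It estimates two or three extra quantities. Below r of about 0.2 with baseline and period terms, or about 0.3 with an unneeded leg term as well, it loses a little power.

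It is also fair to say that r and the effect size are assumptions, and that a pre-video VAS reading is not shown to exist. Finally, the document is written in the past tense and justifies the random intercept by large variance in pain tolerance. Data may already have been seen, in which case a change is a reanalysis.

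**Conclusion.** The concern holds in limited form. The plan does not define what the paired t-tests compare, and neither plausible reading adjusts for the same-session pre-video value. The consequence is lost precision and exposure to chance imbalance; validity is not at issue. Under the assumptions above, adjustment for baseline and period gains about 2 points of power at r = 0.3, 10 at r = 0.5 and 23 at r = 0.7 over a post-only test, and loses about 2 points at r = 0. Against a plain change score, it gains about 16, 10 and 3 points at r = 0.3, 0.5 and 0.7. Where the trial falls in this range depends on a correlation that the documents do not give. The mixed model as listed does not fill the gap.

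**What to change.** 1. For each outcome, state the time point and the quantity compared. State whether pain tolerance and VAS were read before and after the video on day 2.
2. For post-video and 24-hour pain tolerance and VAS, and for post-video PANAS, regress the comedy-minus-documentary difference on the comedy-minus-documentary difference in the day-2 pre-video reading, where one was taken. Add a period term coded −1/+1 and, for tolerance and VAS, a leg term coded the same way. The intercept at zero pre-video difference is then the video effect. With 0/1 coding it would instead be the effect for one sequence or leg. The leg term requires that video order and leg order were randomized separately, which the plan should state.
3. Alternatively, for pain tolerance, add treatment-by-time and period terms to the existing mixed model and test the treatment-by-time contrast. That contrast is a difference of changes, so it shares the change score's loss at r below 0.5. It also needs a random effect for session within participant, so that its standard error reflects the within-session correlation.

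The cost is two or three degrees of freedom and a small power loss if r is low. No new participants or visits are needed where the pre-video reading exists. If the results have already been seen, report the adjusted analysis as post hoc alongside the planned test.

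### Bonferroni for the gated pairwise comparisons of the three pain tests is valid but needlessly conservative; Holm's step-down method gives the same family error control within each model and at least as much power

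*Combined protocol and SAP*

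**What the plan says.** The section on the preliminary study sets out to compare "changes in blood pressure and heart rate in response to 3 commonly-used pain tolerance tests". The three are "blood pressure cuff occlusion, blunt force application on muscles, and cold pressor test". The stated purpose is "In order to select the optimum pain tolerance protocol that would not evoke substantial hemodynamic responses".

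The Statistical analyses section gives the method: "To compare physiological changes caused by each pain tolerance test, linear mixed models were used", with a random intercept per participant. Then "ANOVA tables for each fitted model were constructed", and finally "In the case of significance, multiple comparisons were performed using the Bonferroni method". So pairs are examined only after a significant overall test, and each is then held to the full Bonferroni level.

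Four things are not stated: the fixed effects in these models, the number of comparisons in the Bonferroni family, how many of the 40 participants took part in the preliminary study, and any rule that turns pairwise p-values into a choice of test. The significance level ("with the probability level set at $p<0.05") appears only in the sentence on the paired t-tests.

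**The concern.** Two layers of protection are stacked: an overall test, then Bonferroni on every pair. If test is the only factor, there are three pairs, each judged at 0.05/3 = 0.0167. With three means, any two pairwise equalities imply the third. So if the overall null is truly false, at most one pairwise null can be true, and that pair is tested at about 1.7% although 5% would be allowed.

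What is at stake is power for whichever pair of tests has the smaller difference. A difference that Holm would detect at the same family error can go unreported under Bonferroni. This is a loss of efficiency, not an inflated error rate.

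**Working it through.** The plan states no power, effect size, SD or family error for this comparison, so there is no figure of its own to reproduce.

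**Inputs.** From the documents: three tests; a random-intercept model; an overall test before the pairs; Bonferroni; 40 recruited. Assumed: alpha 0.05 two-sided for the overall and pairwise tests; three comparisons per model; SD of change 12 mmHg; correlation 0.3 between tests; mean rises of 5 and 10 mmHg for the close pair; third mean 7.5 to 20 mmHg; n = 10, 20 and 40.

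**Thresholds.** Bonferroni tests every pair at 0.0167 (z = 2.394). Holm tests the smallest p-value at 0.05/3 = 0.0167, the next at 0.05/2 = 0.025 and the largest at 0.05 (z = 1.960), stopping at the first failure. No Holm threshold is below Bonferroni's, so every Bonferroni rejection is also a Holm rejection.

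**Largest possible gain at n = 40 (normal approximation).**
- Residual SD = 12 × √(1 − 0.3) = 10.04 mmHg.
- Standard error of a pair difference = 10.04 × √(2/40) = 2.245 mmHg.
- Standardised difference = 5/2.245 = 2.227.
- Power at the Bonferroni level = Φ(2.227 − 2.394) = Φ(−0.167) ≈ 43%.
- Power at Holm's last step = Φ(2.227 − 1.960) = Φ(0.267) ≈ 61%.

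The ceiling is therefore about 17 points, reached only when the other two pairs are almost sure to be rejected first.

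**Simulation** (20,000 trials per row, overall F test at 0.05, pooled error), power for the 5-versus-10 pair:

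| n | Third mean (mmHg) | Bonferroni | Holm |
|---|---|---|---|
| 40 | 20 | 42% | 59% |
| 40 | 15 | 42% | 54% |
| 40 | 12 | 42% | 48% |
| 40 | 10 | 41% | 44% |
| 40 | 7.5 | 42% | 42% |
| 20 | 20 | 20% | 31% |
| 10 | 20 | 9% | 13% |

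Repeat runs of the first row gave 41 to 42% and 59 to 60%. In the 7.5 mmHg row the gain is about 1 point or less.

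**Error control at n = 40, equal variances.** With means 5/5/20, the false-positive rate for the equal pair is 1.7% with Bonferroni and 5.1% with Holm. With all three equal, the family error is 4.1% for both.

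**Larger families.** With one mean shifted and the rest equal, Holm's family error was 4.1% for four means and 3.9% for six, so it does not rely on there being exactly three.

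**Unequal variances with pooled error.** Take SDs 15/15/8, correlation 0.3, and the two SD-15 tests equal.
- True variance of the equal pair's difference: 225 + 225 − 2 × 0.3 × 225 = 315.
- For each other pair: 225 + 64 − 2 × 0.3 × 120 = 217.
- Pooled value: (315 + 217 + 217)/3 = 249.7.
- The test statistic is inflated by √(315/249.7) = 1.123.
- Actual error at Holm's last step: 2Φ(−1.960/1.123) = 2Φ(−1.745) ≈ 8.1% (simulation 8.2%).
- Actual error with Bonferroni: 2Φ(−2.394/1.123) = 2Φ(−2.131) ≈ 3.3% (simulation 3.3%).
- With pair-specific standard errors, Holm returns to 5.1% in simulation.

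**The case against.** Bonferroni is valid, simple and easy to prespecify, and it gives simultaneous confidence intervals directly, which Holm does not. Intervals suit a criterion about whether a response is large. Its extra margin also absorbs some misspecification: with a pooled error and unequal variances, Bonferroni stays under 5% in the example above and Holm does not. All of this stands. It qualifies any claim that the change is free, but pair-specific errors remove the variance problem, and intervals can be reported alongside.

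Three stronger readings are tempting, and the documents do not support them.

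- *A reader might infer that the choice of outcome test turns on a close comparison between two similar tests.* No section says that two tests respond similarly or that a pairwise p-value decides. The stated criterion concerns the size of each test's own response. Blunt force is already built into the exclusion criteria and is the main-study measure, and nothing shows that another correction would change that choice.
- *A reader might infer that the overall test makes any correction unnecessary.* That holds for exactly three means on one outcome with a sound error term. The plan does not list its fixed effects. If time is also a factor, there are more means, and unadjusted pairs after the overall test gave family errors of 12% with four means and 29% with six (all but one equal).
- *A reader might infer that the preliminary study as a whole is over-corrected.* At least two outcomes, blood pressure and heart rate, are analysed with no stated correction across them. The conservatism is shown only within each model.

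**Conclusion.** The point holds as a minor matter of efficiency. Within each model, Bonferroni after the overall test spends less error than it is allowed, and Holm recovers power at the same family error. The size is uncertain: about 1 to 17 points at n = 40, largest when the third test is far from the other two, and about 4 points at n = 10 (9% to 13%). These figures rest on the assumed SD, correlation, means and sample sizes, none of which the documents supply. Holm's dominance over Bonferroni does not depend on them; its error control requires valid pairwise p-values, hence the condition on standard errors. The comedy-documentary comparison is not affected.

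**What to change.** In the Statistical analyses section, name Holm's step-down method in place of Bonferroni for the pairwise comparisons, with pair-specific standard errors if variances differ between the pain tests. Do not move to unadjusted pairs, because the family size is not stated. In the same sentence, list the fixed effects and the comparisons that form the family.

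The cost is one phrase and one software option; the existing pairwise p-values can be re-adjusted without new data. The price is the loss of simple simultaneous intervals and a thinner margin if a pooled error is kept with unequal variances. Reporting each test's mean change with its confidence interval offsets the first and speaks more directly to the stated purpose, since a non-significant pairwise difference, however adjusted, does not show that two tests are alike.
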